Based upon evidence that EGFR inhibition enhances the cellular response of radiation and cytotoxic chemotherapy, RTOG 0522 tested whether the anti-EGFR antibody, cetuximab, improves disease-free survival over radiation plus concurrent cisplatin. Initial report of the results of this study showed that the addition of cetuximab to radiation-cisplatin did not improve progression-free survival (PFS) or overall survival (OS) (Ang 2011). Failure of cetuximab to improved outcome may be due to insufficient synergistic effect of cetuximab or possibly due to inadequate duration of anti-EGFR therapy. No differential effect was observed based upon p16 status; however, testing was not possible for nearly half of oropharynx patients.

While the importance of EGFR in HNSCC has been well established, a direct role of HER2 in tumorigenesis and treatment resistance of HNSCC is not clear and poorly understood. HER2 is expressed in the range of 0-47% in HNSCC depending on the antibodies used, staining conditions, and scoring systems of immunohistochemistry (IHC) [Kearsley 1991; Beckhardt 1995; Field 1992; Craven 1992; Ibrahim 1997; Khan 2000; Cavalot 2007]. Hou, et al. has shown that HER2 expression progressively increased as oral disease progresses from normal mucosa, pre-malignant lesions to invasive oral SCC (Hou 1992); however, its association with tumor stage, locoregional control, and survival as a prognostic marker varies depending on the sample size and evaluation methods (Craven 1992; Ibrahim 1997; Khan 2002; Cavalot 2007). In a recent study by Cavalot, et al. (2007), a high membranous HER2 protein expression was an independent prognostic factor for disease free survival. To date, HER2 expression has never been evaluated as a predictive biomarker of HER2-specific inhibitor therapy in HNSCC.

In addition, there is a strong rationale of dual-targeting of EGFR and HER2. There is evidence that heterodimers containing HER2 as a partner is the most potent combination for the receptor activity compared to other dimers formed by 4 family members of HER receptors (Arteaga 2003). Inhibitory effects of one receptor have shown to be negated by heterodimers formed by the rest of uninhibited HER receptor family members (Diermeier 2005; Motoyama 2002). The extent of EGFR-HER2 and HER2-HER3 heterodimerization in HNSCC is not known; however, potentially

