As discussed in the following section, lapatinib appears to enhance the effects of chemoradiation. Pilot data suggests that this effect may be more pronounced in p16 negative HNSCC patients. This study will, therefore, test a proof of biologic principle that a potent inhibitor of the EGFR and HER2 signaling pathways can enhance the efficacy of a chemoradiation regimen. In addition, there has never been a study evaluating the HER2 status as a predictive marker of HER2 inhibitors in HNSCC; the proposed study will allow us to evaluate this question, which can only be answered in a clinical trial setting with a control arm. The results of this study also are pertinent to the design of a future phase III clinical trial and development of novel therapeutic regimens and biomarkers.

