1.6 Correlative Studies

While the importance of EGFR in HNSCC has been well established, a direct role of HER2 in tumorigenesis and treatment resistance of HNSCC is not clear and is poorly understood. HER2 is expressed in the range of 0-47% in HNSCC depending on the antibodies used, staining conditions and scoring systems of immunohistochemistry (IHC). Hou, et al. have shown that HER2 expression progressively increased as oral disease progresses from normal mucosa, pre-malignant lesions to invasive oral SCC; however, its association with tumor stage, locoregional control, and survival as a prognostic marker varies depending on the sample size and evaluation methods. In a recent study by Cavalot, et al., a high membranous HER2 protein expression was an independent prognostic factor for disease-free survival. To date, HER2 expression has never been evaluated as a predictive biomarker of HER2-specific inhibitor therapy in HNSCC. Biologic correlative studies of the TryHard study will address these important scientific questions as permitted by the study design that includes a randomized control arm.

Dual-targeting of EGFR and HER2 also provides a strong rationale for the use of lapatinib with chemoRT for LA-HNSCC. There is evidence that heterodimers containing HER2 as a partner is the most potent combination for the receptor activity compared to other dimers formed by 4 family

members of HER receptors. Inhibitory effects of 1 receptor have shown to be negated by heterodimers formed by the rest of uninhibited HER receptor family members. The extent of EGFR-HER2 and HER2- HER3 heterodimerization in HNSCC is not known; however, potentially heterodimerization may occur and contribute to resistance given EGFR-specific tyrosine kinase inhibitors. Therefore, a dual inhibition using lapatinib warrants further investigation and will be examined in the correlative studies.

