1.6.1 HER2 Expression as a Predictive Biomarker of Lapatinib Response

Since lapatinib is a dual inhibitor of both EGFR and HER2, it is logical to evaluate HER2 protein expression and gene amplification in addition to the EGFR analysis and HPV assay (for oropharynx only). For this aim, we propose the following:

- HER2 protein expression determined by image-guided quantification of IHC staining (Cavalot 2007);
- HER2 gene amplification determined by FISH (Khan 2002).

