2.2 Secondary Objectives

2.2.1 To evaluate if the addition of lapatinib to concurrent cisplatin and radiation in this patient population improves overall survival (OS);

2.2.2 To evaluate if the addition of lapatinib to concurrent cisplatin and radiation in this patient population improves control of distant metastasis;

2.2.3 To evaluate toxicity and tolerability between treatment arms;

2.2.4 To evaluate if the addition of lapatinib to concurrent cisplatin and radiation in this patient population improves local regional control;

2.2.5 To investigate quality of life and patient-reported outcomes between treatment arms;

2.2.6 To explore HER2 expression, amplification and heterodimerization, EGFR ligand expression, EGFR polymorphisms, hypoxia, and EMT characteristics as biomarkers of lapatinib response, sensitivity, and resistance, PFS, and metastasis.

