13.0 STATISTICAL CONSIDERATIONS

13.1 Primary Endpoint

13.1.1 Progression-free survival (PFS)

13.2 Secondary Endpoints

- 13.2.1 Overall survival;
- 13.2.2 Distant metastasis;
- 13.2.3 Adverse events;
- 13.2.4 Compliance with planned treatment;
- 13.2.5 Local-regional control;
- 13.2.6 Quality of life and patient-reported outcomes;
- 13.2.7 HER2 expression, amplification and heterodimerization, EGFR ligand expression, EGFR polymorphisms, hypoxia, and EMT characteristics as biomarkers of lapatinib response, sensitivity, and resistance, PFS, and metastasis.

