For analysis of local-regional control, distant metastasis, PFS, and OS, we will examine whether patients with normal baseline levels of biomarkers have a different prognosis than patients with abnormal baseline levels by calculating the product-limit estimates of the survival function and comparing those estimates using the log-rank statistic. The relationship between local-regional control, distant metastasis, PFS, OS, and abnormal baseline marker levels also will be explored by fitting Cox proportional hazards regression models, both adjusted for baseline disease and patient characteristics and unadjusted. Assuming usable baseline tissue/blood samples can be obtained from 118 eligible patients (~75%), this will provide at least modest power (>69%) to detect large differences (hazard ratios > 2.0) between patients with normal and abnormal marker levels, assuming 50% abnormal prevalence, with a two-sided 5% alpha, for the PFS endpoint.

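### The protocol sets out to find markers that predict who benefits from lapatinib, but its only biomarker analysis is prognostic: no treatment-by-marker estimate is specified

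*Combined protocol and SAP*

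**What the plan says.** Objective 2.2.6 is to explore HER2, EGFR and EMT measures "as biomarkers of lapatinib response, sensitivity, and resistance, PFS, and metastasis". Section 13.2.7 repeats this among the secondary endpoints: "EGFR polymorphisms, hypoxia, and EMT characteristics as biomarkers of lapatinib response, sensitivity, and resistance". The aim is therefore partly prognostic (PFS, metastasis) and partly predictive (response, sensitivity, resistance).

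The rationale treats the predictive part as a reason for the design. Sections 1.1 and 1.6 note that "HER2 expression has never been evaluated as a predictive biomarker of HER2-specific inhibitor therapy in HNSCC". Section 1.2 calls this a question "which can only be answered in a clinical trial setting with a control arm" and describes the trial's results as "pertinent to the design of a future phase III clinical trial and development of novel therapeutic regimens and biomarkers". Section 1.6 says the correlative studies will address it "as permitted by the study design that includes a randomized control arm". Section 1.6.4 lists validating prognostic significance and determining predictive effect as two separate tasks for the EGFR polymorphisms.

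The analysis text is one paragraph of Section 13.6: "we will examine whether patients with normal baseline levels of biomarkers have a different prognosis than patients with abnormal baseline levels". It uses product-limit estimates and log-rank tests, then Cox models of outcome on marker level, with and without adjustment for baseline covariates. Its power statement is more than 69% for hazard ratios above 2.0 in PFS between normal and abnormal groups, with 118 patients, 50% prevalence and two-sided 5% alpha.

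**The concern.** A prognostic comparison asks whether outcome differs between marker groups. A predictive analysis asks whether the lapatinib hazard ratio differs between them. A marker can be strongly prognostic and say nothing about who benefits, and the reverse also holds. Treatment arm does not appear in the biomarker paragraph, and nothing elsewhere in Section 13 supplies a treatment-by-marker contrast. Adding arm as an adjustment covariate would not supply one either, because a main effect of treatment does not let its effect vary with the marker.

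At stake is a stated secondary objective. The report could show which markers accompany better or worse outcome, with no planned estimate of which patients lapatinib helps. A prognostic result reported under objective 2.2.6 could be misread as evidence on benefit and carried into phase III planning. The samples and randomized arms needed for the missing estimate are already in the design.

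**Working it through.** **Inputs.** 69 PFS events, 158 analyzable patients originally and 128 after revision (Section 13.5). 118 patients with usable samples (about 75%), hazard ratio 2.0, 50% prevalence, two-sided 5% (Section 13.6). Section 13.3 gives two arms but no ratio, so 1:1 is assumed. Sampled patients are assumed to have events at the same rate as all patients.

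**1. Events with marker data.** 69 × 118/158 = 51.5. Under the revised size, 75% of 128 is 96, and 69 × 96/128 = 51.75. Both round to 52, so the sample-size cut does not alter what follows as long as 69 events and a 75% sample share hold.

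**2. The plan's own figure.** Marker main effect, two equal groups: power = Φ(√(d/4) × ln 2 − 1.96) = Φ(3.589 × 0.693 − 1.96) = Φ(0.53) = 0.70. This matches the stated value. Within one arm (d = 25.8) it would be Φ(2.538 × 0.693 − 1.96) = Φ(−0.20) = 0.42. The figure therefore fits a prognostic test on all sampled patients.

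**3. The missing estimate at 50% prevalence.** With four equal cells, the variance of the log ratio of hazard ratios is 16/d, four times the main-effect variance of 4/d. SE = √(16/51.5) = 0.557.
- Power for a ratio of 2.0: Φ(0.693/0.557 − 1.96) = Φ(−0.72) = 0.24.
- 95% interval: estimate divided and multiplied by exp(1.96 × 0.557) = 2.98.
- Simulated Cox fits (exponential times, 96 or 118 patients, stopped at 52 events, Wald test of the interaction) give about 21–24%.
- For a ratio of 4.0 the formula gives 70%, but simulation gives about 60–67%, so the formula is optimistic for large interactions.

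**4. At an assumed 25% prevalence.** SE = √(4/(51.5 × 0.25) + 4/(51.5 × 0.75)) = 0.643, which gives power of 0.19. This formula spreads events by prevalence alone. If the smaller, marker-positive group benefits more from lapatinib, it contributes fewer events and power falls. Simulated power for a ratio of 2.0 is about 10–14% in that direction (up to 16% in some settings) and about 20% if the marker-positive group benefits less. A single figure without the direction would mislead.

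**5. Curves for the competing-risk endpoints.** The general text of Section 13.6 estimates distant metastasis and local-regional control by cumulative incidence, to allow for competing risks, and compares arms by cause-specific log-rank. Section 13.4 defines the competing events. The biomarker paragraph uses product-limit estimates for the same two endpoints. A product-limit curve that censors competing events does not estimate the cumulative incidence used elsewhere. The log-rank and Cox comparisons can stand as cause-specific, so only the descriptive curves are affected. The documents do not give what is needed to size the difference.

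**The case against.** The strongest reply is that this is an exploratory objective on optional samples. The primary endpoint, error rate and go/no-go rule are untouched, and the added result would be too imprecise to settle anything. All of that is true, and it limits the weight of the point. It does not remove it: exploratory status relaxes demands on power and multiplicity, but it does not turn a prognostic contrast into a predictive one. Low power is a reason to report an estimate with its interval and to say so plainly. Narrowing 2.2.6 and 13.2.7 to prognosis would also restore consistency, but it would give up the question that Section 1.2 says needs a control arm.

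A reader might infer more than the documents support:
- That the plan states the arms will be pooled. It does not; pooling is inferred from the absence of any mention of arm and from the power figure.
- That the stated power is wrong. It is right for the test it describes.
- That the absence of a cut-point for abnormal, of a lead HER2 assay, of continuous coding or of a named hypoxia assay is an error of the same kind. The protocol text gives no general cut-point, but its assays cite published methods that cannot be checked here. The rest are design choices.
- That post-baseline marker values would be misused. The paragraph is already limited to baseline levels.

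**Conclusion.** The mismatch is real. Objective 2.2.6 and endpoint 13.2.7 have a predictive part, the rationale rests it on randomization, and the only specified analysis is prognostic. No estimate of how the lapatinib effect varies by marker would follow from the plan as written.

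The remedy will be imprecise. Assuming 1:1 arms and about 52 events, power for a ratio of hazard ratios of 2.0 is about 21–24% at 50% prevalence. At an assumed 25% it is about 10–14% or about 20%, depending on direction. It would be wrong to read the added model as able to prove or exclude a predictive marker. The competing-risk point is smaller and concerns descriptive curves only. Neither point bears on the trial's primary conclusion.

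**What to change.** Add to Section 13.6 an exploratory Cox model for PFS with treatment, baseline marker and treatment-by-marker terms. Apply it to the markers that Section 1.6 proposes as predictive: HER2 protein and amplification, EGFR and EGFR-HER2 dimers, EGFR ligands, EGFR polymorphisms and EMT markers. LOX and Gli1 are proposed only for distant metastasis and are not included. Report the lapatinib hazard ratio by marker level and the interaction, each with a 95% confidence interval. State the low power given above and that the analysis is exploratory. Keep the existing normal-versus-abnormal comparison as the prognostic analysis.

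Separately, replace the product-limit curves by marker group for local-regional control and distant metastasis with cumulative incidence curves, and label the log-rank and Cox comparisons for these endpoints as cause-specific.

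Naming a lead HER2 assay in advance, coding markers as continuous, fixing cut-points and naming the hypoxia assay are optional refinements.

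The cost is a few sentences and routine model output, with no new patients, visits or samples. The downside is wide intervals, about three-fold each way at 50% prevalence, which must be stated with the results so that they are not over-read.

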1.6.2 EGFR-HER2 Heterodimer Expression as a Predictive Biomarker of Lapatinib Response

Activation of EGFR involves either homodimerization or heterodimerization between EGFR and HER2. The in situ proximity ligation assay (PLA) was developed to enable detection of individual proteins and protein-protein interactions in cell lines and tissues, specifically paraffin embedded tissues (Söderberg 2006; Weibrecht 2010). The approach uses oligonucleotides attached to the antibodies against the 2 target proteins, in this case, pEGFR and pHer2. The oligonucleotides on the proximity probes when brought into close proximity by protein dimerization, serve as templates for the circularization, which can then be amplified and visualized as bright fluorescent RCPs or colometric RCP dots (depending on the type of detection). Since each detected protein dimerization gives rise to one RCP, the detected complexes can be easily enumerated and counted. Tissue PLA has been used to assay for HER-family dimerization in tissue samples using the Duolink Kit from Olink Bioscience (Uppsala, Sweden). We have also evaluated pEGFR dimerization in head and neck squamous cell carcinoma and found that this approach can be readily applied to tissue microarray of formalin-fixed, paraffin-embedded tumor tissues. We propose to use this assay to evaluate EGFR homodimerization and EGFR-HER2 heterodimerization on pretreatment tumor samples as a potential predictor for lapatinib efficacy.

1.6.3 EGFR Ligand Expression Levels in Tissue and Blood as a Predictive Biomarker of Lapatinib Response

mRNA expression of EGFR ligands such as TGFA, AREG, EREG, and HB-EGF have been shown to correlate with prognosis in HNSCC (Grandis 1998) and predict for efficacy of EGFR targeting, specifically cetuximab in colorectal cancer (Khambata-Ford 2007; Hatakeyama 2010). Based on this information, we propose to evaluate the following EGFR ligand expression levels as a biomarker predictor of lapatinib response: TGFA, AREG, EREG and HB-EGF mRNA levels determined by RT-PCR (Grandis 1998; Khambata-Ford 2007; Hatakeyama 2010). In addition, we will measure HB-EGF (one of the EGFR ligands) protein levels in plasma samples collected at pre-, end-of-radiation, and post-treatment (Hatakeyama 2010).

1.6.4 Variant EGFR 497 Arg Allele and EGFR Intron 1<20 CA Repeats as a Prognostic Biomarker of Poor Relapse-Free Survival and a Predictive Biomarker of Lapatinib Sensitivity

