Variant EGFR 497 Arg allele and EGFR intron 1<20 CA repeats have been shown to be a prognostic biomarker of poor relapse-free survival (RFS) in HNSCC. However, its role in predicting lapatinib sensitivity is unknown in these patients. Since these polymorphisms can be readily measured from circulating WBC, we propose to evaluate these allelic variants in patients enrolled on this study, both to validate their prognostic significance as well as to determine their predictive effect of lapatinib response. The following assays will be performed:

- Assess EGFR gene polymorphism 497 arginine-to-lysine determined by PCR-RFLP using germline DNA collected from pre-treatment PBMC (Zhang 2005);
- Assess EGFR intron 1 CA repeat polymorphisms determined by PCR-RFLP using germline DNA collected from pre-treatment PBMC (Amador 2004).

1.6.5 Validation of Lysyl Oxidase (LOX) and Gli Family Zinc Finger (Gli1) as Biomarkers of Distant Metastasis

We have previously identified LOX and Gli1 as biomarkers for distant metastasis in HNSCC treated with radiation alone on RTOG 90-03 (Le 2009, Chung 2010). The role of these markers in HPV negative patients treated with chemoradiation has not been evaluated. We propose to validate the role of these biomarkers as predictors for distant metastasis by quantifying the level

of these proteins in pre-treatment tumor samples (as previously described in Le 2009 and Chung 2010).

1.6.6 Epithelial-to-Mesenchymal Transition (EMT) as a Prognostic Biomarker of Poor RFS and a Predictive Biomarker of Lapatinib Resistance

EMT is a well known process governing invasion and metastasis in epithelial cell tumors. Although several biomarkers have been suggested to reflect the EMT process, one common hallmark of EMT is increased vimentin expression in the tumor (Frederick 2007). Recently, certain microRNAs, including miR-212, miR-103 and miR-200 have been linked to the EMT process, and their expression levels have been correlated with poor outcomes (Hatakeyama 2010; Martello 2010). In this exploratory study, we proposed to measure EMT by the following 2 approaches and determine whether the levels of these EMT biomarkers correlate with poor RFS and/or lapatinib resistance in the treated patient population.

- Vimentin expression in pre-treatment tumors determined by automated quantitative analysis (AQUA) (Frederick 2007);

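### Section 13.6 analyses quantitative baseline biomarkers only as normal versus abnormal, gives no cut-off for them and shows power at 50% prevalence alone; a continuous Cox term would use more of the data at almost no cost

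*Combined protocol and SAP*

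**What the plan says.** Section 13.6 sets out two prognostic analyses of baseline markers for local-regional control, distant metastasis, PFS and OS. The first is a log-rank comparison: "we will examine whether patients with normal baseline levels of biomarkers have a different prognosis than patients with abnormal baseline levels". The second uses the same grouping: "abnormal baseline marker levels also will be explored by fitting Cox proportional hazards regression models", with and without covariate adjustment. No continuous marker term is described.

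The power statement takes 118 patients with usable samples (about 75%) and claims more than 69% power for hazard ratios above 2.0, "assuming 50% abnormal prevalence, with a two-sided 5% alpha, for the PFS endpoint".

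Section 1.6 chooses assays that mostly yield quantities:
- 1.6.1: "HER2 protein expression determined by image-guided quantification of IHC staining"
- 1.6.2: counted proximity-ligation dimer signals
- 1.6.3: "TGFA, AREG, EREG and HB-EGF mRNA levels determined by RT-PCR", and plasma HB-EGF protein
- 1.6.5: LOX and Gli1 protein levels
- 1.6.6: vimentin by automated quantitative analysis, and circulating microRNAs

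Neither Section 1.6 nor Section 13 gives a cut-off, or a rule for choosing one, for any of these. Section 1.6 also reports that "HER2 is expressed in the range of 0-47% in HNSCC depending on the antibodies used, staining conditions and scoring systems". Section 2.2.6 words the biomarker objective as exploratory.

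**The concern.** Reducing a measured level to two groups discards the ordering within each group. With only about 52 events expected among patients with samples, that loss is not trivial. Because the groups are undefined for the quantitative assays, the analysis cannot be reproduced from the document, and the expected share of abnormal patients is unknown. Power is shown only at the even split, so a reader cannot see what happens if abnormal levels are uncommon. Section 1.2 says the results bear on the design of a later phase III trial and on biomarker development, so a real association missed here has some cost.

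**Working it through.** **Inputs.** From Section 13.5: 69 PFS events, 158 evaluable patients originally and 128 analysable after revision. From Section 13.6: 118 patients with samples, hazard ratio 2.0, two-sided 5%, 50% prevalence. The plan does not give the number of events among patients with samples, so I assume they are proportional: 69 × 118/158 = 51.5.

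**Step 1: reproduce the plan's figure.** Schoenfeld power = Φ(ln(HR) × √[d·p(1−p)] − 1.96).

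With d = 51.5 and p = 0.50: ln 2 × √(51.5 × 0.25) = 2.488, and Φ(2.488 − 1.96) = 70.1%. This agrees with the stated figure of over 69%. After the sample-size revision, 75% of 128 is 96 patients and 69 × 96/128 = 51.75 events, which gives 70.3%. The revision therefore leaves the figure unchanged, provided 69 events are reached.

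**Step 2: vary the prevalence.** The term p(1−p) is largest at p = 0.50. The table gives power (%) for a hazard ratio of 2.0 by formula, and for a simulated log-rank test (118 patients, 52 events, exponential times, 40,000 runs per cell) in each direction of effect.

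| Abnormal prevalence | Formula | Simulated, abnormal doubles hazard | Simulated, abnormal halves hazard |
|---|---|---|---|
| 50% | 70 | 70 | 69 |
| 47% | 70 | 71 | 68 |
| 42% | 69 | not run | not run |
| 40% | 68 | 71 | 64 |
| 30% | 63 | 69 | 54 |
| 25% | 58 | 67 | 48 |
| 20% | 51 | 62 | 40 |
| 10% | 32 | 46 | 13 |

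By formula, power falls below 69% under about 42% prevalence. In simulation, if abnormal doubles the hazard, power stays near 69% down to about 30% and then falls. If abnormal halves the hazard, power is below the formula throughout.

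**Step 3: information kept by a split.** This is the squared correlation between the marker and its two-group version. For a normal marker cut at c, it is φ(c)²/[p(1−p)]. At the median, 0.3989²/0.25 = 0.637 (= 2/π), so about 36% is lost. A median split of a uniform marker keeps 0.75 (25% lost); of an exponential marker, 0.48 (52% lost). For a normal marker the loss grows with imbalance: 42% at a 30% split and 66% at a 10% split.

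**Step 4: what that means for power.** Take a normal marker whose median split has the Step 1 signal of 2.488. As a continuous term the signal is 2.488/√(2/π) = 3.118, and Φ(3.118 − 1.96) = 87.7%. The matching effect is ln 2/(2√(2/π)) = 0.434 per SD, a hazard ratio of about 1.54 per SD. Simulation (118 patients, 52 events) at 0.45 per SD gives 70.4% split and 88.6% continuous; at 0.43 it gives 66.5% and 85.9%. The gain is 18 to 19 points in both.

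**The case against.** The strongest reply is that the plan's power sentence is right and open about its condition, and that the work is exploratory: only PFS by treatment arm decides on a phase III trial. Both points stand. Section 1.6.6 also speaks of EMT marker levels correlating with relapse-free survival, which does not itself impose a split. That is a statement of intent, though, and Section 13.6 provides no analysis to carry it out. LOX and Gli1 are to be measured as in cited work whose cut-offs, if any, cannot be seen here.

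Four stronger readings are tempting, and the documents do not support them.
- *The power figure is wrong.* It reproduces at 70.1%.
- *The power fails across the protocol's own 0-47% HER2 range.* By formula it still holds at 42-47%. That range is also a spread across published assays and scoring systems, not the abnormal prevalence under this trial's quantified assay.
- *The 50% can come only from a median split made after seeing the data.* Section 13.6 states 50% as a planning assumption and mentions no median.
- *Dichotomising inflates false positives.* A median split ignores outcome; a fixed even split with no effect rejected in 5.2% of simulated trials. Only a cut chosen on outcome would inflate the error, and the plan proposes none. The absence of a rule leaves that open but does not amount to planning it.

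The loss of about 36% depends on the assumed shape. A marker with many zero values would not be normal, and a plain log transform would not suit it.

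**Conclusion.** The point holds as a cheap improvement in method, not as an error in the plan. Section 13.6 describes only a two-group analysis of markers that are largely measured as quantities, and it does not define the groups for them. On an assumed normal marker with a log-linear effect and about 52 events, a median split costs about 36% of the information (25% to 52% for other assumed shapes), or about 70% power where a continuous term would give about 88%. The power of over 69% is valid at 50% prevalence. At lower prevalence it falls by formula to 63% at 30%, 51% at 20% and 32% at 10%, with the exact fall depending on the direction of effect.

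The point does not apply to markers that are categorical by nature: HER2 amplification by FISH if read as a category, EGFR 497 genotype, and the intron 1 repeat marker, which has its own cut-off of fewer than 20 repeats. It concerns the prognostic analysis only; a continuous main effect does not answer whether a marker predicts benefit from lapatinib. Since the objective is exploratory, the priority is modest.

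**What to change.** In Section 13.6:
- Make the main prognostic analysis of each quantitative assay a Cox model with the suitably transformed level as a continuous covariate, reported as a hazard ratio per SD, with a spline check of linearity. Where many values are zero, add a positive/negative indicator.
- Keep groups for the categorical markers named above and for display. State how each group is defined, with any cut-off fixed without reference to outcome.
- Beside the 50% figure, show grouped-marker power at lower prevalences, for example 30%, 20% and 10%, labelled as illustrative assumptions.

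This changes analysis-plan wording only and needs no further samples or patients. The costs are a linearity assumption, which the spline checks, slightly more analysis work, and a less favourable power statement for uncommon abnormal results.
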